9.1 Statistical Hypothesis

Not applicable. Demographic and baseline characteristics, efficacy, safety, [REDACTED] [REDACTED] [REDACTED] will be summarized descriptively. No inferential testing will be performed.

9.1.1 Multiplicity Adjustment

Not applicable

9.2 Analysis Sets

Efficacy, safety, [REDACTED] [REDACTED] [REDACTED] collected will be summarized for the ITT population.

Participant Analysis Set	Description
Intent-to-treat population (ITT)	All participants enrolled in the study.

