VTAMA will be dispensed and will be administered at home between clinic visits as instructed by site personnel. Application instructions will be reviewed at all clinic visits during the study, except during the final treatment/end-of-study visits. Participants will be instructed to apply cream QD to all affected areas on the head and neck, including the target lesion. Cream should be applied to newly appearing areas on the head and neck as well as areas in this region that improve or clear during the study. Participants may apply cream to any other lesions on the body although efficacy will only be assessed at the target lesion (PGA) [REDACTED]. Participants will apply sufficient cream to cover completely each lesion with a thin layer of medication and will record the time of application in a daily diary provided by the study site. Participants will be instructed to maintain the approximate dosing time chosen at the beginning of the study for their full study participation.

Number of Participants:

Approximately 30 participants will be enrolled.

Note: Enrolled means participants agreement to participate in a clinical study following completion of the informed consent process and screening. Potential participants who are screened for the purpose of determining eligibility for the study, but do not participate in the study, are not considered enrolled, unless otherwise specified by the protocol. A participant will be considered enrolled if the informed consent is not withdrawn prior to participating in any study activity after screening.

Study Arms and Duration:

VTAMA (tapinarof) cream, 1% is a white to off-white cream containing 1% weight/weight (10 mg/g) tapinarof, supplied in 60-gram tubes. VTAMA is to be administered by the participant QD via topical application of a thin layer to affected areas in accordance with instructions in the USPI.

Dosing may be interrupted if deemed necessary by the Investigator for management of AEs.

Study duration:

- The study duration will be up to 17 weeks.
- The treatment duration will be up to 12 weeks.
- The follow-up period will be up to 1 week.

Statistical Methods

Efficacy, safety, [REDACTED] [REDACTED] [REDACTED] [REDACTED] will be summarized for the ITT population.

Every effort will be made to collect complete data at all visits. All efficacy data will be summarized based on OCs. The primary and exploratory efficacy endpoints will also be summarized utilizing the last observation

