6.2 Preparation, Handling, Storage, and Accountability

1. The Investigator or designee must confirm appropriate conditions (e.g., temperature) have been maintained during transit for all study product received, and any discrepancies are reported and resolved before use of the study product.
2. Only participants enrolled in the study may receive study product, and only authorized site staff may supply study product.

3. All study product must be stored in a secure, environmentally controlled, and monitored (manual or automated) area in accordance with the labeled storage conditions with access limited to the Investigator and authorized site staff.
4. The Investigator or authorized site staff is responsible for study product accountability, reconciliation, and record maintenance (i.e., receipt, reconciliation, and final disposition records).
5. Further guidance and information for the final disposition of unused study products are provided in the Study Reference Manual.

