5. STATISTICAL CONSIDERATIONS

5.1. General Considerations

will perform the statistical analysis of the data. SAS version 9.4 or higher will be used to generate all statistical outputs (tables, listings, figures [TLFs], and datasets). The International Council for Harmonisation (ICH) numbering convention will be used for all TLFs. Continuous endpoints will be summarized by presenting the number of observations, means, standard deviations, medians, minimums, and maximums. The 95% confidence intervals will be reported as appropriate.

Time to event analyses will use the Kaplan-Meier product limit method (if estimable) based on observed cases.

Categorical endpoints will be summarized by presenting counts and percentages of subjects in corresponding categories. 95% confidence intervals will be reported using Clopper Pearson method as appropriate. When summarizing categorical variables, all possible categories as defined in the case report form (CRF) will be populated, even if they have zero counts. With the exception of ethnicity and race in the demographic table, percentages for missing values are omitted and do not account for the percent calculation of other categories. In certain tables (e.g., TEAEs), the total number of subjects is used as denominator. Footnotes will specify the percent basis in those cases.

will be computed and reported within EDC following the computation method outlined in protocol Section 10.6.

CONFIDENTIAL Page 9/21

Individual subject data obtained from the eCRFs and any derived data will be presented by subject in data listings.

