5.2. Analysis Populations

The intent-to-treat (ITT) population will include all participants enrolled in the study.

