8. SAFETY ASSESSMENTS

8.1. Extent of Exposure

The following exposure and compliance parameters will be summarized descriptively by treatment:

- Total number of days exposed, defined as date of last dose of study drug date of first dose of study drug + 1.
- Number of doses administered will be calculated from the in-clinic dose at Baseline, the subject dose diary and number of missed doses from the summary of missed doses form. If a subject is exposed to study drug for more than 1 day, and returns no diary records, then the total number of doses is regarded to be missing. Otherwise, for any day for which there is no diary record, it is assumed that no study drug was administered at home.
- Percent compliance will be calculated as the (Number of Doses Administered) / (Number of Days Exposed) * 100.
- Subject compliance, defined as ≥80% compliance while enrolled in the study. If the percentage of study medication compliance cannot be computed, the subject is assumed to be less than 80% compliant.

A subject will be compliant with the dosing regimen if they applied \geq 80% of the expected doses. Expected number of doses is based on length of time enrolled in the treatment-phase of the study.

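### Safety is summarised on all enrolled participants, with no dosed (safety) set, so anyone enrolled but never dosed would dilute the TEAE percentages; the effect is conditional and probably zero or small

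*Protocol*

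**What the plan says.** Protocol 9.2 names one analysis set, ITT, described as "All participants enrolled in the study". The sentence above that table covers efficacy and safety together and says the data "collected will be summarized for the ITT population". SAP 5.2 agrees: "The intent-to-treat (ITT) population will include all participants enrolled in the study". Neither document defines a set based on dosing.

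The Protocol synopsis (Number of Participants) defines enrolment. "Enrolled means participants agreement to participate in a clinical study following completion of the informed consent process and screening". It adds: "A participant will be considered enrolled if the informed consent is not withdrawn prior to participating in any study activity after screening". A dose is not part of either sentence. Protocol 6.2 puts enrolment before dosing: "Only participants enrolled in the study may receive study product".

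On the safety side, SAP 5.1 says: "In certain tables (e.g., TEAEs), the total number of subjects is used as denominator". SAP 8.2 restricts AE summaries to TEAEs, meaning events after dosing or pre-existing events that worsened. SAP 8.1 computes days exposed from first and last dose dates and percent compliance as doses divided by days exposed. It then states: "If the percentage of study medication compliance cannot be computed, the subject is assumed to be less than 80% compliant".

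**The concern.** The safety derivations assume a first dose but the population they run on does not. An enrolled participant who never applies cream adds one to the TEAE denominator and ordinarily nothing to the numerator. That person has no days exposed, so compliance cannot be computed, and the default rule would put them in the non-compliant group although they never started treatment.

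Any distortion of the TEAE percentages would run downward, in the product's favour, in a study whose stated intent (Protocol 9.3.1) includes showing a favourable safety profile. The disposition summary in SAP 6.1 lists screened, ITT, treatment completers, study completers and reasons for discontinuation. It has no count of participants dosed, so the appropriate safety denominator would not be stated directly.

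**Working it through.** The plan gives no figure to reproduce. Thirty participants is a choice on clinical grounds (Protocol 9.5, SAP 4), and no TEAE or compliance rate is stated.

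**Inputs**
- N = 30 enrolled (Protocol synopsis, approximate).
- u = participants enrolled but never dosed. The documents give no value; u = 0 to 3 is an assumption.
- x = participants with a TEAE. The values 0, 9 and 15 are illustrative.
- Intervals are 95% Clopper-Pearson, the method named in SAP 5.1, and are given for scale.

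**Formulas**
- Percentage as planned: x/N. Percentage among dosed: x/(N − u).
- Ratio of planned to dosed: (N − u)/N = 1 − u/N, so the relative understatement is u/N. For u = 1, 2, 3 this is 1/30 = 3.3%, 2/30 = 6.7%, 3/30 = 10.0%.

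**Results**

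| u | Dosed | Relative dilution | x = 9: planned | x = 9: dosed (95% CI) | x = 15: planned | x = 15: dosed |
|---|---|---|---|---|---|---|
| 0 | 30 | 0% | 30.0% | 30.0% (14.7 to 49.4) | 50.0% | 50.0% |
| 1 | 29 | 3.3% | 30.0% | 31.0% (15.3 to 50.8) | 50.0% | 51.7% |
| 2 | 28 | 6.7% | 30.0% | 32.1% (15.9 to 52.4) | 50.0% | 53.6% |
| 3 | 27 | 10.0% | 30.0% | 33.3% (16.5 to 54.0) | 50.0% | 55.6% |

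The gap is therefore 1.0 to 3.3 percentage points at a reported 30%, and 1.7 to 5.6 points at a reported 50%, for one to three undosed participants.

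With no events (x = 0), the upper confidence limit is 11.6% on 30 participants, against 11.9%, 12.3% and 12.8% on 29, 28 and 27.

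For compliance, suppose every dosed participant is compliant and the default rule is applied to the undosed. The compliant share then reads 29/30 = 96.7%, 28/30 = 93.3% or 27/30 = 90.0% instead of 100%.

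**Is u > 0 possible under the text?** Yes, but the opening is narrow. Enrolment takes effect with post-screening study activity. The first application is supervised at Visit 2 (Protocol 6.5), and SAP 8.1 refers to an in-clinic dose at Baseline. What clearly remains is an eligible participant who begins that visit and leaves before applying cream.

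**The case against.** A reader might go further and infer that the plan builds in undosed participants: that someone whose target lesion no longer scores PGA 2 to 4 at Baseline, or who has a positive pregnancy test, is already enrolled and so sits in ITT without a dose. The documents do not support this. Both are entry requirements (Protocol 5.1). The synopsis says that people screened for eligibility who do not take part are not counted as enrolled. Protocol 5.4 treats failure to meet the participation criteria as screen failure, and waivers are barred. These people most naturally fall outside ITT. The pregnancy test is required before the first dose, but its visit is left to the schedule of activities, which is not in the text available here.

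Other points on that side also stand:
- An undosed participant is not strictly excluded from the TEAE numerator, because SAP 8.2 counts an AE with a completely missing start date as a TEAE.
- SAP 8.1 names no population. Its default for compliance that cannot be computed fits a dosed participant who returned no diary. Applying it to someone never exposed is an inference from ITT being the only set.
- The analysis is descriptive with no testing, so no decision rule changes. The shift is small against the sampling uncertainty at this size.
- Dilution could be worked out indirectly. The number of observations for days exposed would show how many were dosed, the ITT count is reported, and AEs are listed by participant.

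None of this closes the gap. The screen-failure definition turns on entry to the study, not on dosing, and the enrolment definition still does not require a dose.

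**Conclusion.** The point holds as a minor, conditional one. ITT is the only set, it is expressly used for safety, and membership does not require a dose, while the TEAE, exposure and compliance derivations do. Each enrolled but undosed participant among 30 would lower TEAE percentages by a relative 3.3%. With none, the two denominators coincide and nothing changes.

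It would be too strong to say that TEAE rates or compliance are biased downward as a matter of fact. The documents give no number undosed, the range 0 to 3 is assumed, and the supervised first dose together with the screen-failure rule makes zero or a very small number likely. The TEAE effect rests on reading the total number of subjects in SAP 5.1 as the ITT count, which Protocol 9.2 supports. The compliance effect rests on the further inference that ITT also governs SAP 8.1.

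**What to change.** Add to Protocol 9.2 and SAP 5.2: *Safety population: all participants who applied at least one dose of study product.* Name it as the denominator throughout SAP Section 8 (exposure, compliance and TEAEs). Keep ITT for efficacy. Add a line to the disposition summary in SAP 6.1 for participants enrolled but not dosed.

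The cost is one definition and one extra population flag. TEAE percentages may come out slightly higher; if all enrolled participants are dosed, these percentages do not change.

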9.3 Statistical Analyses

9.3.1 General Considerations

This study is intended to show that VTAMA (tapinarof) cream, 1% has a favorable safety and efficacy profile when applied to lesions in the head and neck region over a 12-week dosing period.

Objectives and endpoints are provided in Section 3.

Every effort will be made to collect complete data at all visits. All efficacy data will be summarized based on OCs. The primary and exploratory efficacy endpoints will also be summarized utilizing the last observation carried forward method to impute missing data [REDACTED] [REDACTED] [REDACTED]

9.3.2 Primary Endpoint Analysis

The primary efficacy endpoint will be summarized descriptively with frequency count, percentage, and 95% confidence interval.

9.3.3 Secondary Endpoint Analysis

The Kaplan-Meier product limit method will be used to estimate the median time to achieving a target lesion PGA score of 0 or 1 with a ≥ 2 -grade improvement from Baseline (if estimable).

9.3.4 [REDACTED]

9.3.5 Safety Analyses

The number and percent of participants with TEAEs will be summarized by system organ class, and preferred term for all TEAEs; all TEAEs by system organ class, preferred term, and maximum CTCAE grade; all TEAEs considered by the Investigator to be related to study product; SAEs; TEAEs leading to study product discontinuation; and TEAEs leading to discontinuation from study.

9.4 Interim Analysis

Not applicable

9.5 Sample Size Determination

The sample size for this study is based on clinical considerations only. No formal sample size calculation will be performed. A total of 30 participants is planned for this study which is considered adequate to evaluate the efficacy and safety for the treatment of plaque PSO in the head and neck region.

10 Supporting Documentation and Operational Considerations

10.1 Appendix 1: Regulatory, Ethical, and Study Oversight Considerations

10.1.1 Regulatory and Ethical Considerations

- This study will be conducted in accordance with the protocol and with the following:
 - Consensus ethical principles derived from international guidelines including the Declaration of Helsinki and Council for International Organizations of Medical Sciences international ethical guidelines
 - Applicable ICH GCP guidelines
 - Applicable laws and regulations
- The protocol, protocol amendments, ICF, IB, and other relevant documents (e.g., advertisements) must be submitted to an IRB/IEC by the Investigator and reviewed and approved by the IRB/IEC before the study is initiated.
- Any amendments to the protocol will require IRB/IEC approval before implementation of changes made to the study design, except for changes necessary to eliminate an immediate hazard to study participants.
- Protocols and any substantial amendments to the protocol will require health authority approval prior to initiation (if applicable per country- or region-specific regulations) except for changes necessary to eliminate an immediate hazard to study participants.
- The Investigator will be responsible for the following, as applicable:
 - Providing written summaries of the status of the study to the IRB/IEC annually or more frequently in accordance with the requirements, policies, and procedures established by the IRB/IEC
 - Notifying the IRB/IEC of SAEs or other significant safety findings as required by IRB/IEC procedures
 - Providing oversight of the conduct of the study at the site and adherence to requirements of 21 CFR, ICH guidelines, the IRB/IEC, European regulation 536/2014 for clinical studies, European Medical Device Regulation 2017/745 for clinical device research, and all other applicable local regulations

10.1.2 Financial Disclosure

Investigators and Sub-investigators will provide the Sponsor with sufficient, accurate financial information as requested to allow the Sponsor to submit complete and accurate financial certification or disclosure statements to the appropriate regulatory authorities. Investigators and Sub-investigators are responsible for providing information on financial interests during the course of the study and for 1 year after completion of the study.

10.1.3 Informed Consent Process

- The Investigator or the Investigator's representative will explain the nature of the study, including the risks and benefits, to the potential participant and answer all questions regarding the study.
- Potential participants must be informed that their participation is voluntary. Participants will be required to sign a statement of informed consent that meets the requirements of 21 CFR 50, local regulations, ICH guidelines, privacy and data protection requirements, where applicable, and the IRB/IEC or study center.
- The medical record must include a statement that written informed consent was obtained before the participant was enrolled in the study and the date the written consent was obtained. The authorized person obtaining the informed consent must also sign the ICF.

- Participants must be reconsented to the most current version of the ICF(s) during their participation in the study.
- A copy of the ICF(s) must be provided to the participant.

Participants who are rescreened are required to sign a new ICF.

10.1.4 Data Protection

- Participants will be assigned a unique identifier by the Sponsor. Any participant records or datasets that are transferred to the Sponsor will contain the identifier only; participant names or any information which would make the participant identifiable will not be transferred.
- The participant must be informed that their personal study-related data will be used by the Sponsor in accordance with local data protection law. The level of disclosure must also be explained to the participant who will be required to give consent for their data to be used as described in the informed consent
- The participant must be informed that their medical records may be examined by Clinical Quality Assurance auditors or other authorized personnel appointed by the Sponsor, by appropriate IRB/IEC members, and by inspectors from regulatory authorities.
- The contract between Sponsor and study sites specifies responsibilities of the parties related data protection, including handling of data security breaches and respective communication and cooperation of the parties.
- Information technology systems used to collect, process, and store study-related data are secured by technical and organizational security measures designed to protect such data against accidental or unlawful loss, alteration, or unauthorized disclosure or access.

10.1.5 Dissemination of Clinical Study Data

Anonymized Clinical Study Reports will be disclosed as required by regulatory authorities.

Study information and tabular study results will be posted on National Institutes of Health's website www.clinicaltrials.gov and other publicly accessible sites. Study results may be published in peer-reviewed publications or presented at scientific meetings.

Following an assessment of a rigorously defined research question from a third party, Dermavant may grant access to analyzable datasets from this study through a secure system.

10.1.6 Data Quality Assurance

- All participant data relating to the study will be recorded on printed or electronic CRFs unless transmitted to the Sponsor or designee electronically (e.g., laboratory data). The Investigator is responsible for verifying that data entries are accurate and correct by physically or electronically signing the CRF.
- Guidance on completion of CRFs will be provided in CRF completion guidelines.
- The Investigator must permit study-related monitoring, audits, IRB/IEC review, and regulatory agency inspections and provide direct access to source documents.
- Monitoring details describing strategy, including definition of study critical data items and processes (e.g., risk-based initiatives in operations and quality such as risk management and mitigation strategies and analytical risk-based monitoring), methods, responsibilities, and requirements, including handling of noncompliance issues and monitoring techniques (central, remote, or on-site monitoring) are provided in the Study Reference Manual.
- The Sponsor or designee is responsible for the data management of this study, including quality checking of the data.

- The Sponsor assumes accountability for actions delegated to other individuals (e.g., contract research organizations).
- Records and documents, including signed ICFs, pertaining to the conduct of this study must be retained by the Investigator for 15 years after study completion unless local regulations or institutional policies require a longer retention period. No records may be destroyed during the retention period without the written approval of the Sponsor. No records may be transferred to another location or party without written notification to the Sponsor.

10.1.7 Source Documents

- Source documents provide evidence for the existence of the participant and substantiate the integrity of the data collected. Source documents are filed at the Investigator's site.
- Data reported on the CRF or entered in the eCRF that are transcribed from source documents must be consistent with the source documents or the discrepancies must be explained. The Investigator may need to request previous medical records or transfer records, depending on the study. Also, current medical records must be available.
- Definition of what constitutes source data and its origin can be found in source data acknowledgment.
- The Investigator must maintain accurate documentation (source data) that supports the information entered in the eCRF.
- The Sponsor or designee will perform monitoring to confirm that data entered into the CRF by authorized site personnel are accurate, complete, and verifiable from source documents; that the safety and rights of participants are being protected; and that the study is being conducted in accordance with the currently approved protocol and any other study agreements, ICH GCP, and all applicable regulatory requirements.

